1.3. Statistical Hypothesis

The general form of duration of effect hypotheses will be:

H_o: β = 0H_A: β < 0

where $\exp(\beta)$ is the hazard ratio (experimental treatment / comparator treatment) for loss of effect. The study is not powered for formal hypothesis testing and any analyses presented will be for interpretation purposes only.

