7. STATISTICAL METHODS

7.1. Primary Effectiveness Endpoint

The primary effectiveness endpoint will be duration of effect (regardless of responder status), defined as the number of days from Treatment Day (Baseline) to the day that GLS severity (Investigator assessment) at maximum frown returns to the Baseline value. Although the trial is not powered for inferential analysis, this will be the most influential outcome in the overall assessment of the effectiveness of prabotulinumtoxinA 40 Units, compared to prabotulinumtoxinA 20 Units, in treating moderate to severe glabellar lines. Analysis will be performed using the modified Intent-To-Treat (mITT) population and regardless of responder status.

Duration of effect will be described by Kaplan-Meier curves and the respective median times with associated 2-sided 95% confidence interval (CI) for each treatment group. Statistical analyses of treatment group differences will be done using Cox proportional hazards regression with time to return to Baseline as the dependent variable, treatment group as the independent variable, and age, gender, and Baseline GLS score (Investigator assessment) at maximum frown as covariates.

Statistical significance will be established at the 0.025 level with one-sided hypothesis testing.

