7.5.1. Modified Intent-to-Treat Population

The mITT Population is defined as all subjects who were randomized, received their injection of IP, and have at least one post-dosing assessment for the primary effectiveness endpoint. The ITT principle will be followed in that subjects in the mITT population will be analyzed according to the treatment assigned as per the randomization schedule. The mITT Population will be the primary population used for effectiveness analyses of primary, secondary, tertiary, and exploratory effectiveness endpoints.

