7.5.2. Per-Protocol Population

The PP Population is defined as treated subjects who complete the entire study up to the final visit with no protocol deviations that could affect effectiveness assessments. The decision whether a protocol violation/deviation is relevant for the exclusion of subjects from the PP Population will be made in a data review meeting prior to breaking the study blind. The PP Population will be used for supportive effectiveness analyses.

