7.6. Sample Size Considerations

This study is not powered for inferential analyses. Approximately 150 subjects will be randomized to the study, 50 subjects in each of the three treatment arms; 20U onabotulinumtoxinA, 20U prabotulinumtoxinA and 40U prabotulinumtoxinA. Assuming 50 subjects per treatment group, exponential distributions for failure and censoring times, a median duration of effect of 4 months in the reference group, and an annual censoring rate of 10%, the study will have 80% power to detect a hazard ratio of 0.47 based on a one-sided hypothesis test of the primary effectiveness endpoint with alpha = 0.025. As such, it is the opinion of the study Sponsor that 50 subjects per group (total sample size n=150) will be sufficient to address the objectives of this study.

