7.7. General Considerations

Data will be listed by subject number. Data will be summarized by treatment and study visit, where applicable. For categorical parameters, the number and percentage of subjects/observations in each category will be presented; percentages will be based on the number of subjects in the relevant analysis population in each treatment group. For continuous parameters, descriptive statistics will include n (number of subjects or observations), mean, standard deviation, median, and range. A full description of the statistical methods planned for this study will be provided in the Statistical Analysis Plan (SAP). All programs for data output and analyses will be written in SAS version 9.4 or higher (SAS Institute, Inc., Cary, NC).

Missing Values: For the mITT analysis of primary, secondary, tertiary, and exploratory duration of effectiveness endpoints, in the case of a missed visit, subjects will be considered to have returned to Baseline if they are confirmed to have returned to Baseline at the next non-missed visit. Subjects will be considered to have to have returned to Baseline if they fail to attend 2 consecutive visits or drop out of the study. For missing observations for exploratory endpoints other than duration of effect data will be analyzed as observed without imputation.

Discontinuation and Drop-Outs: Dropouts will not be replaced. Subject disposition will summarize the number of subjects who were randomized and who discontinued from the study (including reasons for discontinuation).

Interim Analysis: An interim analysis will be conducted when >90% of subjects have completed Visit 8 (Day 120) to evaluate response to exposure (efficacy, duration) and adverse events. For assessment of the primary effectiveness endpoint, 95% CIs will be presented but statistical analyses will not be conducted and a statistical penalty for the final analysis will not be employed. While data by treatment group will be presented, individual subjects will not be unblinded.

Poolability of Investigative Sites: Data from all investigative sites will be pooled based on the assumption of clinical comparability: the same protocol will be used for all sites, all sites will be monitored for protocol compliance, and the same data collection instrument and methodology will be used across all sites.

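### SAP 7.7 counts dropouts and two-visit gaps as returned to Baseline even when the observed Investigator GLS is still improved, gives that event no date, and plans no analysis that censors them

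*SAP*

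**What the plan says.** - **Endpoint.** SAP 7.1 defines duration of effect as "the number of days from Treatment Day (Baseline) to the day that GLS severity (Investigator assessment) at maximum frown returns to the Baseline value". SAP 2.3 adds that effect lasts for as long as severity has not gone back to its Baseline grade.
- **One missed visit.** SAP 7.7 counts a return only "if they are confirmed to have returned to Baseline at the next non-missed visit".
- **Two missed visits, or dropout.** The same paragraph says mITT subjects are "considered to have to have returned to Baseline if they fail to attend 2 consecutive visits or drop out of the study". No observed return is required. Protocol 12.8 has the same wording.
- **Power statement.** SAP 7.6 assumes exponential failure and censoring times "and an annual censoring rate of 10" percent.
- **Decision rule.** SAP 7.1: "Statistical significance will be established at the 0.025 level with one-sided hypothesis testing". SAP 1.3 says that "any analyses presented will be for interpretation purposes only".
- **Populations.** mITT subjects must "have at least one post-dosing assessment for the primary effectiveness endpoint". The Per-Protocol set is "treated subjects who complete the entire study up to the final visit" without relevant deviations, and is supportive.
- **Data available.** Protocol 11.3 asks withdrawn subjects to attend an Early Termination visit, and Protocol 10.2.6 records Investigator GLS there.
- **Output.** Table 14.3.1.1 has one event row and one censored row. Neither document dates an imputed return or plans a run that censors dropouts. The only sensitivity analyses mentioned are post hoc ones for COVID-19 disruption (Protocol 12.8).

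**The concern.** The rule can set aside the measurement that defines the endpoint. A subject who misses two visits and is then seen still improved is scored as returned, while a subject who misses one visit and is then seen still improved is not. A subject who leaves with an improved Early Termination GLS is also scored as returned.

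Counting dropout as an event is a legitimate choice, but it makes the endpoint a composite. SAP 7.1 does not say so, and SAP 7.6 plans on the opposite treatment. Table 14.1.2 also counts discontinuations before return to Baseline; SAP 7.7 scores those same mITT subjects as having returned.

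At stake are the hazard ratio and medians for what SAP 7.1 calls the most influential outcome. If dropout differs by arm, part of that difference appears as a treatment difference, in whichever direction the imbalance runs.

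**Working it through.** **Inputs.** From SAP 7.6: 50 per arm, reference median 4 months, hazard ratio (HR) 0.47, 10% annual loss, one-sided 0.025. Follow-up of 12 months comes from SAP 2.1. Dropout rates other than 10% are assumptions, and dropout is taken as independent of return.

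**Step 1: the plan's figure.** Monthly hazards: reference h = ln2/4 = 0.1733; 40U h = 0.47 × 0.1733 = 0.0814. Loss d = −ln(0.9)/12 = 0.00878. Observed events per arm = 50 × h/(h+d) × [1 − exp(−12(h+d))], which gives 42.2 + 29.9 = 72.1. Power ≈ Φ(√(E/4) × |ln HR| − 1.96) = 89.3% (Schoenfeld); Freedman's formula gives about 86.5%. The stated 80% is not reproduced, because SAP 7.6 states no follow-up or accrual time; about 7 to 8.25 months of follow-up would give it. The stated figure is therefore conservative, and this does not affect the point.

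**Step 2: dropout scored as an event.** Each arm's hazard becomes h + d, so HR = (h40 + d40)/(href + dref) and the median is ln2/(h + d). Imputed events per arm = 50 × d/(h+d) × [1 − exp(−12(h+d))].

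At 10%/10%: HR = (0.0814 + 0.0088)/(0.1733 + 0.0088) = 0.496.

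| True HR | Annual dropout, reference/40U | Imputed events, reference/40U | HR under rule | Medians, months | Power or error: censored → rule |
|---|---|---|---|---|---|
| 0.47 | 10%/10% (plan) | 2.1 / 3.2 | 0.496 | 3.81 / 7.68 (true 4.00 / 8.51) | power 89.3% → 87.1% |
| 0.47 | 5%/15% (assumed) | 1.1 / 4.8 | 0.535 | 3.90 / 7.30 | power 89.4% → 78.9% |
| 1 | 20%/10% (assumed) | 4.4 / 2.1 | 0.949 | 3.61 / 3.81 | error 0.025 → 0.0435 |
| 1 | 30%/10% (assumed) | 6.7 / 2.1 | 0.897 | 3.41 / 3.81 | error 0.025 → 0.074 |

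**Step 3: simulation on the visit schedule.** 50 per arm, visits at Days 30 to 330 and 365, Cox model with Efron ties, 3,000 to 6,000 runs. At 10%/10%, power was 0.888 censored and 0.871 to 0.882 under the rule. At 5%/15%, 0.898 and 0.776 to 0.816. One-sided error with no true difference: 20%/10%, 0.020 to 0.026 censored and 0.037 to 0.046 under the rule; 30%/10%, 0.021 to 0.023 and 0.067 to 0.073.

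**Step 4: does the Per-Protocol set show the shift?** Dropouts removed, 3,000 runs each:

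| Dropout, reference/40U | HR censored | HR under rule | HR Per-Protocol | Share of shift kept by Per-Protocol |
|---|---|---|---|---|
| 10%/10%, true 0.47 | 0.469 | 0.495 | 0.475 | 0.006/0.026 = 23% |
| 5%/15%, true 0.47 | 0.467 | 0.533 | 0.493 | 0.026/0.066 = 39% |
| 20%/10%, true 1 | 0.995 | 0.945 | 0.958 | 0.037/0.050 = 74% |
| 30%/10%, true 1 | 1.000 | 0.897 | 0.923 | 0.077/0.103 = 75% |

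Per-Protocol error in the last two rows is 0.039 and 0.052.

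**Step 5: two-visit rule alone.** No dropout, visits missed at random (assumed). At 10% missed, about 1.7 reference and 2.9 40U subjects per 50 whose effect continues are scored as returned; HR 0.469 → 0.496, power 0.898 → 0.862. At 5% missed, about 0.5 and 0.8; HR 0.468 → 0.475. Counting only those who re-attend still improved gives 1.4 and 2.5 at 10%, and 0.4 and 0.7 at 5%.

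**Step 6: event date.** Dating the event at the last attended, first missed or second missed visit gives HR 0.496, 0.492 or 0.490 at 10%/10%, and 0.542, 0.534 or 0.526 at 5%/15%.

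**The case against.** The strongest reply is that the rule is prespecified in both documents, is a recognised composite, and is mildly conservative at the only dropout rate the documents give. Power stays above the stated 80%. That is right, and it limits the weight of the point. The unequal rates are assumed; blinding of subjects and evaluators makes large imbalance less likely, though not impossible.

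A second reply is that censoring can be the worse analysis. Protocol 4.1 offers no-cost treatment after exit, so some subjects may leave because the effect has worn off. Suppose, with no true difference, 10% of reference returns and 20% of 40U returns go unobserved because the subject leaves at that moment. Censoring then gives HR 0.8/0.9 = 0.89, falsely favouring 40U, while the SAP rule gives 1.0. The simulations above cannot show this because they assume non-informative dropout. This stands: the censored run belongs beside the primary rule and does not have to replace it. It does not justify scoring as returned someone later seen still improved.

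Third, an improved Early Termination GLS does not contradict a return after that visit. This also stands. Direct conflict with an observation is confined to re-attendance after a gap, which is few subjects, and unscheduled visits (Protocol 10.2.7) can recover some missed assessments.

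Fourth, Tables 14.1.2 to 14.1.4 show dropout and attendance by arm, and Per-Protocol is a supportive analysis; SAP 7.7 states its rule for mITT, so Per-Protocol may also escape the two-visit imputation. These help. They reveal an imbalance, but not how far it moved the hazard ratio, and Per-Protocol keeps part of the shift when dropout is unequal. Dropouts with no post-dose primary assessment are outside mITT and unaffected.

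**Conclusion.** The concern holds and should be fixed; it is not fatal. At the plan's equal 10% dropout, the rule moves the hazard ratio from 0.47 to about 0.50, shortens the medians by about 0.2 and 0.8 months, and costs about 2 points of power. If dropout differs by arm, the shift can favour or penalise 40U and can be material: one-sided error of roughly 0.04 to 0.07 in the two null cases, or power near 79% at 5%/15%. Those figures rest on assumed rates, exponential times and dropout independent of return. Because SAP 1.3 limits the analyses to interpretation, the shift in the hazard ratio and medians matters more than the error rate. The missing event date matters little to the hazard ratio at planned dropout (a spread of 0.006) and needs only clarification.

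**What to change.** 1. In SAP 7.7, after two or more missed visits take status from the next observed Investigator GLS, with no event if it is still improved. Treat the subject as a dropout only if no later GLS exists.
2. If dropout is deliberately an event, keep it as primary and say so in SAP 7.1.
3. In either case, prespecify one run of the primary model that censors dropouts at the last Investigator GLS, including the Early Termination GLS.
4. Split the event row of Table 14.3.1.1 into observed and imputed returns by arm.
5. State in one line the date given to an imputed event.

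The cost is a few sentences, one extra model run and one split table row; no new data are needed. The censored run assumes non-informative dropout, as SAP 7.6 already does, so it should be read alongside the primary result. Item 1 changes primary scoring. SAP 7.7 plans an interim that presents data by treatment group, so the amendment should record whether by-arm results had been seen when the rule was changed. Items 3 to 5 leave the classification of primary events unchanged, although item 5 fixes the timing of imputed ones.

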### 10.2.5 Visits 5 to 15 (Visits each 30 Days; V5 $\pm$ 3 days, V6 to V15 $\pm$ 7 days)

Subjects will continue to be monitored for safety and effectiveness at one-month intervals. On and after **Day 90**, subjects are eligible to exit the study once their GLS score at maximum frown has returned to Baseline (Investigator assessment). Subjects will return for monthly assessments until they reach their Baseline GLS score (Investigator assessment). Assessment procedures include:

- Brow Area Photography
- Effectiveness Evaluations Investigator (Blinded Evaluator)
  - GLS (max frown)
  - GAIS
- Effectiveness Evaluations Subject
  - GLS (max frown)
  - GAIS
  - Subject Satisfaction
  - Clinical Interview (Visit 5; Day 30 only) (Section 10.3.4)
- Safety Assessments Investigator (Blinded Evaluator)
  - Directed Questionnaire
  - Directed Review of Systems
  - Vital Signs
  - Physical Exam
  - Concomitant Medications
  - Adverse Events

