### 10.2.6 Visit 16 (Final Visit or ET Visit; Day 365 ±14 days)

The Final visit (or ET visit) will take place when subjects GLS score (Investigator assessment) has returned to Baseline. Subjects may withdraw from participation in the study at any time for any

reason. If withdrawal occurs, the subject should be asked to complete a follow-up or early termination visit, if possible. During the final or early termination visit, both safety and effectiveness evaluations will be performed as follows:

- Brow Area Photography
- UPT (if female subject of childbearing potential)
- Effectiveness Evaluations Investigator (Blinded Evaluator)
  - GLS (max frown)
  - GAIS
- Effectiveness Evaluations Subject
  - GLS (max frown)
  - GAIS
  - Subject Satisfaction
  - Clinical Interview
- Safety Assessments Investigator (Blinded Evaluator)
  - Directed Questionnaire
  - Directed Review of Systems
  - Vital Signs
  - Physical Exam
  - Clinical Laboratory Tests
  - ECG
  - Concomitant Medications
  - Adverse Events

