2. OVERVIEW OF STUDY DESIGN

2.1. Study Design

This is a multicenter, prospective, randomized, double-blind, active-controlled, single-treatment, increasing dose design.

Approximately 150 subjects will be randomized 1:1:1, to either 20U onabotulinumtoxinA, 20U prabotulinumtoxinA-xvfs, or 40U prabotulinumtoxinA-xvfs. Subjects with moderate or severe glabellar lines at maximum frown on the 4-point validated Glabellar Line Scale (*GLS*, 0=none, 1= mild, 2=moderate, 3=severe), as judged by the investigator and the subject, will be eligible.

Safety and effectiveness will be assessed on days 3, 7, and 30, then every 30 days up to 365 days or until the subject has returned to Baseline as assessed by the Investigator, at which point the subject will exit the study. Please refer to Table 1 below for visit specifics.

Duration of effect will be estimated by Kaplan-Meier analysis and will be based on the number of days from Treatment Day (Baseline) to the day that GLS severity (Investigator assessment) at maximum frown returns to the Baseline value (i.e., the treatment will be considered to remain effective for the amount of time during which GLS severity at maximum frown has not returned to Baseline severity).

The Evaluating Investigator (i.e., Blinded Investigator) will be responsible for managing the subject, monitor for related and unrelated adverse effects, and carrying out the evaluations. Injections of study drug will be performed by an "Unblinded Injector" (i.e., physician or nurse practitioner not responsible for subject follow-up).

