2.3. Primary Endpoint

The primary effectiveness endpoint will be duration of effect, defined as the number of days from Treatment Day (Baseline) to the day that GLS severity (Investigator assessment) at maximum frown returns to the Baseline value. The treatment will be considered to remain effective for the amount of time during which GLS severity at maximum frown has not returned to Baseline severity. Duration of effect will be estimated by Kaplan–Meier analysis.

Although the trial is not powered for inferential analysis, this will be the most influential outcome in the overall assessment of the effectiveness of prabotulinumtoxinA 40 Units, compared to prabotulinumtoxinA 20 Units, in treating moderate to severe glabellar lines.

Confidential Page 9/58

TABLE 1. SCHEDULE OF EVENTS AND PROCEDURES

Visit Number	V1 ¹ Screening	V2 ¹	V3	V4 (phone f/u)	V5 to V15 ²	V16 ³ (or Final Visit, or ET)	Unscheduled Visit 11
Day/Week/Month	≤ 14D	Tx Day	48Hr	D 7	D30 to D330 Monthly Visits	D365	
Visit Windows				±1 Day	D30 ±3D, ≥D60 ±7D	±14D	
Assessment and Procedures							
Informed Consent	X						
Inc/Excl Criteria	X						
Demographics, Med Hx	X						
Randomization to Study Tx 4		X					
Effectiveness - Investigator							
Glabellar Line Scale ⁵	X	X	X		X	X	X
Global Aesthetic Improvement			X		X	X	X
Effectiveness - Subject							
Glabellar Line Scale ⁵	X	X	X		X	X	X
7-Day Subject Diary		Х —		—			
Global Aesthetic Improvement			X		X	X	X
Subject Satisfaction Score			X		X	X	X
Clinical Interview 6					D30 only	X	X
Safety Evaluations							
Directed Questionnaire ⁷	X		X		X	X	X
Directed Review of Systems	X		X		X	X	X
Vital Signs 8	X		X		X	X	X
Physical Exam 9	X		X		X	X	X
UPT (as applicable)	X	X				X	
Clinical Laboratory Tests 10	X					X	X
ECG	X					X	X
Safety Assessment Phone Call				X			
Brow Area Photography	X	X	X		X	X	X
Concomitant Medications	X	X	X	X	X	X	X
AE Assessment		X	X	X	X	X	X

- 1. Screening and treatment visit can take place the same day, at the discretion of the investigator
- 2. Subjects will be followed monthly until their Glabellar Line Scale score is back to Baseline (Investigator assessment)
- 3. Subject exits study once their Glabellar Line Scale Score has returned to Baseline (Investigator assessment)
- 4. IP may be administered same day as Screening
- 5. Glabellar Line Scale at Maximum Frown, 0=none, 1=mild, 2=moderate, 3=severe
- 6. Clinical Interview Questions
 - What did you like about the treatment (clinically or other feedback)?

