7.3. Exploratory Effectiveness Endpoints

Exploratory effectiveness endpoints will be evaluated for signals of effectiveness to explore whether any should be elevated in importance for subsequent trials. These endpoints will be assessed using either logistic regression (for binary endpoints) or survival analysis-type methods as described above. Comparisons will be made between all treatment groups. Chi-square tests of association or Fisher's exact tests will be used to compare treatment group differences in proportion of subjects returning to Baseline at each time point in the study. Exploratory endpoints will be:

Version 1.1 31-May-2023 Confidential Page 18/58

- 1. Duration of effect for GLS responders, defined as the number of days from Treatment Day (Baseline) to the day that GLS severity at maximum frown returns to the Baseline value. Analyses will be conducted for Investigator and subject assessments of GLS. Various responder definitions will be tested (1-Point, 2-Point and 3-Point responders at any time during the study; GLS Score of 0 or 1 at any time during the study; 1-Point responders at Day 30).
- 2. Time to loss of GLS responder status, with responder being defined as a GLS score of 0 or 1 at any point during the study. Analyses will be conducted for Investigator and subject assessments of GLS.
- 3. GLS responder rates (Investigator assessments) at each study visit. Various responder definitions will be tested (1-Point, 2-Point and 3-Point responders; GLS Score of 0 or 1; GLS Score 0 or 1 & ≥2-Point improvement; GLS Score 0 or 1 & ≥2-Point improvement & Investigator GLS = subject GLS).
- 4. GLS responder rates (Subject assessments) at each study visit. Various responder definitions will be tested (1-Point, 2-Point and 3-Point responders; GLS Score of 0 or 1).
- 5. GAIS response (score of 2 or 1) as assessed by Investigator and subject at each visit.
- 6. SSS response (score of 2 or 1) as assessed by subjects at each visit.
- 7. Onset of effect as assessed by subjects through the 7-Day Subject Diary.

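### Analysing visit-wise Investigator GLS responder rates as observed drops subjects who exited on return to Baseline, so the later-visit models no longer compare the randomised groups

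*SAP*

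**What the plan says.** **Endpoint and model.** SAP 7.3 item 3 lists "GLS responder rates (Investigator assessments) at each study visit", with definitions of at least 1, 2 or 3 points' improvement, a score of 0 or 1, and combinations of these. On method it says "These endpoints will be assessed using either logistic regression (for binary endpoints) or survival analysis-type methods as described above". It also plans chi-square or Fisher tests to "compare treatment group differences in proportion of subjects returning to Baseline at each time point in the study".

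**Exit.** SAP 2.1 schedules assessments up to Day 365 or "until the subject has returned to Baseline as assessed by the Investigator, at which point the subject will exit the study". Footnote 3 of SAP Table 1 agrees. Protocol 10.2.6 says "The Final visit (or ET visit) will take place when subjects GLS score (Investigator assessment) has returned to Baseline". Protocol 10.2.5 makes subjects eligible to exit on return only from Day 90; SAP 2.1 and Table 1 set no such floor.

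**Missing data.** SAP 7.7 says "For missing observations for exploratory endpoints other than duration of effect data will be analyzed as observed without imputation". Earlier in the same paragraph, subjects who drop out or miss two consecutive visits are counted as returned, but only for duration endpoints.

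**Denominator.** SAP 7.5.1 names mITT as the primary population for exploratory endpoints, and SAP 7.7 bases percentages on the analysis population. The responder shells (Tables 14.3.3.3.1 to 14.3.3.5.1) nevertheless carry an N at each visit, separate from the group n in the header, and place the percentage and the odds ratio in one block.

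**The concern.** The event that ends follow-up is the outcome being analysed. Eligibility requires an Investigator GLS of 2 or 3, so a subject back at Baseline has no improvement and no score of 0 or 1. That subject's status is known at exit, yet has no place in any later visit-wise model. The plan counts drop-outs of unknown status as returned for duration endpoints, but gives no visit-wise status to subjects with an observed return.

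Three things follow at later visits. Absolute rates computed on observed subjects are too high in both arms. The observed sets differ in size between arms, and they differ in composition if any prognostic factor affects duration. A percentage on the mITT denominator may also sit beside an odds ratio from observed subjects only. SAP 7.3 says these endpoints are meant to show what to elevate in later trials, so a distorted late-visit pattern bears directly on their purpose.

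**Working it through.** The plan attaches no figure to the as-observed rule, so there is none to reproduce. Its sample-size assumptions are used to show the size of the effect.

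**Inputs from SAP 7.6:** 50 per arm, exponential times, reference median 4 months (taken as 120 days), hazard ratio 0.47. **Assumed:** Weibull shapes k = 2, 3 and 4 with the same median and hazard ratio; return is permanent; other drop-out is ignored.

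**Formulas.** Response is at least 1 point on Investigator GLS, that is, not yet returned.

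- S(t) = exp(−ln 2 × HR × (t/120)^k), with HR = 1 (reference) or 0.47 (40U).
- Rate among all subjects at visit day d: S(d).
- Rate as observed, from Day 120: S(d)/S(d−30), on 50 × S(d−30) subjects.

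**Day 180 by hand, k = 1.**

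- Reference: S(180) = exp(−0.693 × 1.5) = 0.354; S(150) = exp(−0.693 × 1.25) = 0.420. As observed: 0.354/0.420 = 0.841, on 50 × 0.420 = 21.0 subjects.
- 40U: S(180) = exp(−0.693 × 0.47 × 1.5) = 0.613; S(150) = 0.665. As observed: 0.613/0.665 = 0.922, on 33.3 subjects.
- Odds ratio, all subjects: (0.613/0.387)/(0.354/0.646) = 2.90. As observed: (0.922/0.078)/(0.841/0.159) = 2.23.

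**Results, 40U vs reference.**

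| Shape, day | All subjects | Difference, OR | As observed | Difference, OR | n observed |
|---|---|---|---|---|---|
| k=1, Day 120 | 72% vs 50% | 22 points, 2.6 | 92% vs 84% | 8 points, 2.2 | 39.2 vs 29.7 |
| k=1, Day 180 | 61% vs 35% | 26 points, 2.9 | 92% vs 84% | 8 points, 2.2 | 33.3 vs 21.0 |
| k=1, Day 240 | 52% vs 25% | 27 points, 3.3 | 92% vs 84% | 8 points, 2.2 | 28.3 vs 14.9 |
| k=2, Day 180 | 48% vs 21% | 27 points, 3.5 | 80% vs 62% | 18 points, 2.4 | 30.1 vs 16.9 |
| k=3, Day 180 | 33% vs 10% | 24 points, 4.7 | 63% vs 37% | 26 points, 2.9 | 26.5 vs 12.9 |
| k=4, Day 180 | 19% vs 3% | 16 points, 7.7 | 43% vs 16% | 26 points, 3.8 | 22.6 vs 9.2 |

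A simulation of 400,000 subjects per arm, with return detected at the next 30-day visit and exit from Day 90, gave Day 180 as-observed rates of 92.1% vs 84.2% (k=1), 79.9% vs 62.0% (k=2) and 62.9% vs 37.4% (k=3), in agreement with the formulas.

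Under the plan's exponential model the as-observed pair stays at 92% vs 84% from Day 120 to Day 240, while the true rates fall from 72% vs 50% to 52% vs 25%. The table would show a flat response while the effect wears off. Approximate one-sided power at Day 180 (alpha 0.025) is 17% as observed and 75% with exits counted as non-responders.

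**Loss of balance (assumed trait).** Suppose half of each arm carries a trait that doubles the hazard, with the reference median held at 120 days. Among subjects not returned by Day 150, its share is 43% (40U) vs 35% (reference) for k=1, 41% vs 32% for k=2 and 39% vs 28% for k=3. With a trait hazard ratio of 1.5 to 3, k=1 gives 46% vs 41% to 39% vs 28%.

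**Exit timing.** Anyone returned by Day 90 is gone by Day 120 with or without the Day 90 floor, so the figures from Day 120 hold either way. Days 30 to 90 are unaffected only if the floor applies.

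**The case against.** The strongest counter-argument is that exit on return is completion, not missingness. Table 14.1.2 has a row for subjects who completed up to return to Baseline, separate from discontinuation before return. With mITT as the population and the denominator sentence in SAP 7.7, exited subjects could be meant to stay in. That reading protects the percentages: on an mITT denominator they are not inflated. It does not reach the logistic models, which need a value for each subject at each visit, and no passage supplies one. Under the mixed reading, the Day 180 row for k=1 would print 61% vs 35%, implying an odds ratio of 2.9, beside a modelled 2.2. Covariate adjustment can also separate the two, so a mismatch alone would not prove an error; here it would come from different subject sets.

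Several limits stand. The endpoints are exploratory, the study is declared unpowered for inference, and the primary Kaplan–Meier and Cox analysis already describes duration in the mITT population without this selection. The fall from 26 to 8 points is specific to the exponential model; at shapes 3 and 4 the difference grows. At those shapes the latest visits are nearly empty (2.4 vs 0.1 subjects at Day 240 for k=4), so no model could be fitted there. The trait is hypothetical, and only the at-least-1-point definition was quantified.

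**Conclusion.** The concern holds. Followed as stated, the as-observed rule makes the later visit-wise Investigator GLS models compare sets selected on the outcome after randomisation, of unequal size by arm. At Day 180, in all four shapes, both rates rise, the odds ratio falls and the arms shrink unequally. Whether the difference between arms shrinks or grows depends on the hazard shape and cannot be fixed in advance. These sizes rest on the plan's hazard ratio and median, on the assumed Weibull shapes, and on ignoring other drop-out. That exited subjects are known non-responders who vanish from the models needs none of those assumptions. This should be fixed before the analysis is run; the primary and secondary duration analyses do not depend on it.

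**What to change.** In SAP 7.7, state the following for the visit-wise Investigator GLS responder endpoints:

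- A subject who exited on Investigator-assessed return to Baseline stays in the mITT denominator and in the logistic model at every later visit, as a non-responder.
- The exit assessment (Visit 16 or early termination) is mapped to the visit at which it took place.
- As-observed handling is kept only for visits missed for other reasons.

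Also align the denominator sentence with the per-visit N in the responder shells. State that the proportion returning to Baseline at each time point is cumulative and counts exited subjects as returned; it has no shell at present. Protocol 10.2.5 must be reconciled with SAP 2.1 and Table 1 on when exit may occur, so that the first affected visit is clear. The SAP's statement that it prevails over the protocol makes this more pressing.

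The cost is two rules and some edits to wording and shells, with no new data. The rule assumes no re-improvement after exit. Since Protocol 4.1 allows a further treatment after exit, the SAP should name this as a composite definition in which return to Baseline counts as non-response from then on. Subject GLS, GAIS and SSS lose the same subjects, but Investigator return does not determine their status, so no rule is proposed for them here.
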